### **2.3 BENEFIT-RISK ASSESSMENT**

This drug is inviting for testing in this setting due to its tolerability profile and its route of oral administration. This study addresses an important unmet need in urothelial cancer. In a disease which has seen the successful introduction of no new agents in the past ~20 years and for which outcomes remain dismal especially for high risk patients, development of novel, rational agents like afatinib is desperately warranted.

## **3. DESCRIPTION OF DESIGN AND STUDY POPULATION**

### **3.2 OVERALL STUDY DESIGN AND PLAN**

This continuation phase II study is designed to evaluate whether afatinib has activity in patients with unresectable urothelial cancer who are refractory to prior platinum-based chemotherapy and carry somatic molecular alterations of *ErbB* family genes. Patients must have received prior treatment with a platinum-based regimen administered in the perioperative or metastatic setting and must have evidence of disease progression prior to enrollment.

In this single-arm continuation phase II study, all patients will receive afatinib at a starting dose of 40 mg/day given continuously. Radiographic assessment of responses will be performed via CT or MRI every 8 weeks until disease progression is observed or until drug intolerance. The first portion of this study (non-marker selected; already completed- Figure 1) permitted enrollment of patients without consideration of somatic genomic ErbB status. The continuation portion of this trial (the ‘marker-selected’ phase) will only enroll patients whose tumors harbor *ErbB* family genomic alterations. The trial design for the new cohort of the study is shown in Figure 2.

[figure not shown]

Figure 1: Trial Design for the first portion (non-marker selected phase) of the study

[figure not shown]

Figure 2: Trial design for the new cohort (marker selected phase) of the study

### 3.3 SELECTION OF STUDY POPULATION

#### 3.3.1 Main diagnosis for study entry

3.3.1.1 Patients must have locally advanced or metastatic urothelial cancer that

is not amenable to surgical treatment

3.3.1.2 Patients must have histologically or cytologically confirmed urothelial tract carcinoma. Patients with urothelial carcinoma of the bladder, upper tract, or urethra are eligible.

### 3.3.2 Inclusion criteria

3.3.2.1 Patients must have measurable disease, defined as at least one lesion that can be accurately measured in at least one dimension (longest diameter to be recorded) as  $\geq 20$  mm with conventional techniques or as  $\geq 10$  mm with spiral CT scan. See Section 10.2 (Appendix 2) for the evaluation of measurable disease (RECIST v1.1). Lesions that have been irradiated as the most recent line of treatment are not eligible as RECIST target lesions.

3.3.2.2 Patients must have evidence of disease progression prior to enrollment.

3.3.2.3 All patients must have received a prior platinum-based chemotherapy regimen for treatment of urothelial cancer and must now be considered refractory to platinum-based chemotherapy. Patients may have received the platinum-containing regimen either in the peri-operative or metastatic setting. Patients may have received any number of additional prior therapies, and may have received prior immune therapies.

3.3.2.4 Patients must have tumor evidence of somatic genomic molecular alteration in *EGFR*, *HER2*, *ERBB3*, or *ERBB4*, from a test result generated in a Clinical Laboratory Improvement Amendments (CLIA)-certified laboratory. The tumor tissue sample used to generate the qualifying report must be from a muscle-invasive or higher stage urinary tract cancer specimen (metastatic tissue is also acceptable). Final determination about whether a specific tissue source or molecular genomic finding meets criteria as a qualifying result rests with the central study PI. Germline genomic findings will not be returned to patients.

3.3.2.5 Patients must be 18 years of age or older.

3.3.2.6 ECOG performance status 0-1.

3.3.2.7 Patients must have adequate organ function as defined below:

- absolute neutrophil count  $\geq 1,000/\text{mcL}$
- platelets  $\geq 100,000/\text{mcL}$
- hemoglobin  $\geq 8.5\text{g/dL}$
- total bilirubin  $\leq 1.5$  institutional upper limit of normal (IULN)
- AST(SGOT)/ALT(SGPT)  $\leq 2.5 \times \text{IULN}$
- calculated creatinine clearance  $\geq 30 \text{ mL/min}$  by the modified Cockcroft and

Gault Formula OR glomerular filtration rate  $\geq 30$  mL/min/BSA by Modification of Diet in Renal Disease or CKD-EPI formula

3.3.2.8 Women and men of child-bearing potential must agree to use adequate contraception (hormonal or barrier method of birth control; abstinence) prior to study entry and for the duration of study participation. Should a woman become pregnant or suspect she is pregnant while participating in this study, she should inform her treating physician immediately.

3.3.2.9 Patients must have the ability to understand and the willingness to sign a written informed consent document.

### **3.3.3 Exclusion criteria**

3.3.3.1 Patients may not receive any other anti-cancer treatments while on study. Patients cannot have received another anti-cancer chemotherapy or immunotherapy or radiotherapy or investigational agent within 2 weeks prior to the first dose of study treatment.

3.3.3.2 Patients with untreated known brain metastases, or treated brain metastases that are clinically unstable.

3.3.3.3 Uncontrolled intercurrent illness including, but not limited to, ongoing or active infection, symptomatic congestive heart failure, unstable angina pectoris, or psychiatric illness/social situations that would limit compliance with study requirements.

3.3.3.4 Women known to be pregnant.

3.3.3.5 Women who are breastfeeding and who are unwilling to stop breastfeeding prior to study entry.

3.3.3.6 Patients with known prior HIV-positive status on combination antiretroviral therapy are ineligible because of the potential for pharmacokinetic interactions. Known prior HIV-positive patients with  $CD4^+ \leq 500/\text{mm}^3$  are ineligible because of the potential increased risk of infection. (HIV testing is not required as part of this study).

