**Table 4.1.3.2:1 Dose reduction/dose discontinuation scheme**

AE Type and grade	Action	Dose reduction/ discontinuation scheme
Grade 4 rash	Permanently discontinue afatinib	Permanently discontinue afatinib
Grade $\geq 3$ interstitial lung disease	Permanently discontinue afatinib	Permanently discontinue afatinib
Grade 4 hepatic impairment	Permanently discontinue afatinib	Permanently discontinue afatinib
Grade $\geq 3$ keratitis	Permanently discontinue afatinib	Permanently discontinue afatinib
Grade 2 left ventricular dysfunction (i.e., new resting ejection fraction of 40-50%; OR a 10-19% drop from baseline) 	Pause treatment with afatinib for 14 days and then repeat MUGA scan. If the ejection fraction has resolved to grade 1 or better at the time of the repeat MUGA, study drug will be resumed. If the toxicity has not resolved, afatinib should be permanently discontinued.	If patient was receiving 40 mg, resume treatment at 30 mg  . If patient was receiving 30 mg, resume treatment at 20 mg  . If patient was receiving 20 mg, discontinue afatinib.
Any symptomatic (grade $\geq 3$ ) left ventricular dysfunction 	Permanently discontinue afatinib	Permanently discontinue afatinib
CTCAE grade $\geq 2$ diarrhea persisting for 2 or more consecutive days (48 hours) despite adequate anti-diarrheal medication/hydration	Pause treatment with afatinib until toxicity has recovered to CTCAE grade $\leq 1$ or baseline  . If patient has not recovered to CTCAE grade $\leq 1$ within 14 days, study treatment should be permanently discontinued 	If patient was receiving 40 mg, resume treatment at 30 mg  . If patient was receiving 30 mg, resume treatment at 20 mg  . If patient was receiving 20 mg, discontinue afatinib.
CTCAE grade $\geq 2$ nausea and/or vomiting persisting for 3 or more consecutive days despite anti-emetic treatment/hydration		
CTCAE grade 2 or grade 3 worsening of renal function as measured by serum creatinine, newly developed proteinuria, or newly developed decrease in glomerular filtration rate of more than 50% from baseline		
CTCAE grade 4 worsening of renal function	Permanently discontinue afatinib	Permanently discontinue afatinib

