### **4.2.2 Restrictions**

#### **4.2.2.1 Restrictions regarding concomitant treatment**

Patients may not receive any other anti-cancer treatments while on study (bone-directed supportive therapies such as bisphosphonates or RANKL inhibitors are permitted). Patients cannot have received another anti-cancer chemotherapy or immunotherapy or investigational agent within 2 weeks prior to the first dose of study treatment, and cannot have received radiotherapy within 4 weeks prior to the first dose of study treatment.

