## **6.2 DETAILS OF STUDY PROCEDURES AT SELECTED VISITS**

### **6.2.1 Screening period**

Baseline evaluations are to be conducted within 21 days prior to start of protocol therapy. See the Flow Chart for details of required screening procedures.

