#### **Treatment Registration**

Once the signed informed consent has been obtained, all pretreatment evaluations have been performed, and patient's eligibility has been confirmed by the University of Chicago a patient will be registered on study.

When a potential patient has been identified, notify the CRA via phone or email to ensure a reservation on the study. Reservations for potential subjects will only be held for subjects who have signed consent for that particular study.

To register a patient, the research nurse or data manager must complete the eligibility/registration form and contact the central study office at the University of Chicago ([contact]) or fax a copy of the completed eligibility checklist, signed Informed Consent, medical history documents, and results from the baseline evaluations ([contact]) or email (email preferred) to:

[[contact]](mailto:[contact])

When registering a subject, the following must occur:

- Confirm that the institution has current IRB approval of the correct version of protocol/consent and has an annual update on file.
- Submit all required materials (Eligibility Checklist, Source documentation, & signed consent form) to confirm eligibility and required pre-study procedures to the CRA a minimum of 48 hours prior to the subject's scheduled therapy start date.
- Source documentation includes copies of all original documents that support each inclusion/exclusion criteria. The eligibility checklist does not serve as source documentation but rather as a checklist that original source documentation exists for each criterion.
- Communicate with the above CRA to ensure all necessary supporting source documents are received and the potential subject is eligible to start treatment on schedule. If there are questions about eligibility, the CRA will discuss it with the PI. PI may clarify, but not overturn, eligibility criteria.
- Affiliate sites must confirm registration of subjects by obtaining a subject study ID number from the CRA via phone, fax or email.
- If a subject does not start on the scheduled day 1 treatment date, promptly inform the CRA as the delay in start may deem the subject ineligible and/or require further or repeat testing to ensure eligibility.

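### Radiotherapy washout is 2 weeks in exclusion 3.3.3.1 but 4 weeks in 4.2.2.1, with no rule on which governs, so the 4-week limit is easily overlooked

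*Combined protocol and SAP*

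**What the plan says.** **Radiotherapy.** Exclusion 3.3.3.1 puts radiotherapy in one list with chemotherapy, immunotherapy and investigational agents and gives all of them the same interval: "radiotherapy or investigational agent within 2 weeks prior to the first dose of study treatment". Section 4.2.2.1 repeats the 2-week rule without radiotherapy: "Patients cannot have received another anti-cancer chemotherapy or immunotherapy or investigational agent within 2 weeks prior to the first dose of study treatment". It then adds that they "cannot have received radiotherapy within 4 weeks prior to the first dose of study treatment". The synopsis exclusion list and the flow chart give no washout at all.

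**Registration.** Sections 6.3.1 and 6.3.2 require central registration, with eligibility confirmed by the coordinating centre beforehand. Sites send their material at least 48 hours before the planned start. On what is sent: "Source documentation includes copies of all original documents that support each inclusion/exclusion criteria". On doubtful cases: "If there are questions about eligibility, the CRA will discuss it with the PI. PI may clarify, but not overturn, eligibility criteria". On a missed start date, "the delay in start may deem the subject ineligible and/or require further or repeat testing to ensure eligibility". Section 6.2.1 sets the age limit for screening tests: "Baseline evaluations are to be conducted within 21 days prior to start of protocol therapy".

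**Interstitial lung disease.** Table 4.1.3.2:1 has a permanent-stop row headed "Grade $\geq 3$ interstitial lung disease". Section 4.2.1, in bold, calls for permanent discontinuation once the disease is diagnosed and names no grade. The text below the table lets the investigator pause afatinib for up to 14 days and then reduce the dose for a poorly tolerated grade 2 drug-related event that lasts 7 days or more and is not listed in the table.

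**The concern.** An eligibility limit that has two values is wrong as written, whichever value was meant. The stricter value stands in the treatment chapter under concomitant-treatment restrictions. Someone screening a patient reads section 3.3, where radiotherapy has 2 weeks, and has no evident reason to look for a second limit elsewhere. The registration material is also organised around the inclusion and exclusion criteria, and that list shows only 2 weeks.

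Two outcomes are at stake. A patient may be dosed in breach of 4.2.2.1, which then has to be handled as a deviation. Or the 4-week rule may be noticed only when the start is near, so that treatment slips and some baseline tests expire. The situation is plausible: the protocol expects patients whose latest treatment was radiotherapy (3.3.2.1 and 5.4), and 3.3.5 lets patients consent while still on other anti-cancer therapy.

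The lung disease row has a similar weakness, with a safety consequence. A reader who uses only section 4.1.3.2 could treat a grade 2 case as an unlisted grade 2 event and restart at a lower dose, contrary to 4.2.1. Section 1.2.2 describes the condition as rare and potentially fatal.

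**Working it through.** The plan derives no figure on this point, so the check is a comparison of texts plus day-counting.

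**1. Do the two radiotherapy sentences cover the same thing?**

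| Prior treatment | 3.3.3.1 | 4.2.2.1 |
|---|---|---|
| Chemotherapy | 2 weeks | 2 weeks |
| Immunotherapy | 2 weeks | 2 weeks |
| Investigational agent | 2 weeks | 2 weeks |
| Radiotherapy | 2 weeks | 4 weeks |

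The reference point is the first dose in both, and only radiotherapy differs. The target-lesion rule in 3.3.2.1 and 5.4 governs which lesions are measured, not the washout, so it does not reconcile them. No other text gives either section precedence.

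**2. Width of the conflict.** Let d be whole days from last radiotherapy to first dose, with limits of 2 × 7 = 14 and 4 × 7 = 28 days.

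- If the boundary day counts as inside the limit, a patient passes 3.3.3.1 and fails 4.2.2.1 when 14 < d ≤ 28: days 15 to 28, which is 14 days.
- If it does not count, the condition is 14 ≤ d < 28: days 14 to 27, which is 14 days.
- Common to both readings: days 15 to 27, which is 27 − 15 + 1 = 13 days.

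**3. Longest added wait for a patient who already meets 2 weeks.**

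- Boundary day counts: the earliest passing day is 15 and day 29 is needed, so 29 − 15 = 14 days.
- Boundary day does not count: 28 − 14 = 14 days.

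**4. Effect of that wait on screening tests.** A test done a days before the planned start is a + 14 days old after the longest wait. It remains valid if a + 14 ≤ 21, that is a ≤ 7. Tests done more than 7 days before the planned start would have to be repeated. This is the worst case; a shorter wait expires fewer tests.

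**5. Interstitial lung disease by grade.**

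| Grade | Table 4.1.3.2:1 | Text below the table | Section 4.2.1 |
|---|---|---|---|
| 1 | No stop rule | Not covered | Permanent stop on diagnosis |
| 2 | No stop rule | Pause, then reduced dose, if drug-related, prolonged and poorly tolerated | Permanent stop on diagnosis |
| 3 or higher | Permanent stop | Not covered | Permanent stop on diagnosis |

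Stopping at any grade obeys all of these texts. The mismatch is confined to grades 1 and 2, and only at grade 2 does another text offer a competing action.

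**The case against.** The strongest reply is that the two sentences can be obeyed together. Both are prohibitions. Exclusion 3.3.3.1 does not authorise dosing at 3 weeks; it merely fails to exclude it. A site that follows the whole protocol applies 4 weeks. One coordinating centre must also confirm every patient before registration, and a doubtful case can go to the PI for clarification. This stands, and it limits the harm.

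A reader might infer that two sites, both following the protocol, could reach opposite decisions on the same patient. The documents do not support that: a site dosing inside 4 weeks has missed 4.2.2.1, and central confirmation limits divergence at registration. What remains is that confirmation does not say which interval is applied, and a query arises only if someone sees both sentences.

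A reader might also infer that nothing would ever prompt such a query. That cannot be established, because the eligibility checklist is not among the documents. If it carries 4 weeks, most of the practical gap at registration closes. The claim has to stop at the text that can be read.

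Nor do the documents support a claim that the result would be biased. They do not say how many candidates fall in the window, and lesions irradiated as the latest line of treatment are already barred as target lesions.

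For lung disease, the reply is that the table's silence on grades 1 and 2 contradicts nothing, because 4.2.1 already supplies the rule. That is fair for grade 1. It is weaker for grade 2, where the rule for unlisted events gives a different instruction.

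**Conclusion.** The inconsistency is real and should be corrected, but it is a drafting defect in an eligibility rule and not a flaw in the statistical design. Its extent is 13 whole days on any reading, or 14 with the boundary day settled. The consequence is a risk of oversight: deviations from 4.2.2.1, or a start delayed by up to 14 days with some baseline tests repeated. The two-stage design of 29 and then 72 patients, its boundaries and the primary endpoint are untouched.

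The lung disease row merits correction on safety grounds, limited to grades 1 and 2.

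This rests on reading both sections as current, binding text counted from the same first dose. How many patients are affected and what the checklist says are unknown.

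Diarrhea might be put forward as a parallel conflict. The 14-day limit and the default stop are the same in the table and in 4.2.3.1; only the lead-PI clinical-benefit exception in footnote 2 is in tension with the absolute wording of 4.2.3.1. The grade 3 rash text in 4.2.3.3 is in similar tension with that footnote, so correcting diarrhea alone would be incomplete.

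**What to change.** 1. State 4 weeks for radiotherapy in 3.3.3.1 to match 4.2.2.1. Use 2 weeks in both only if the clinical team justifies it. Say whether the boundary day counts.
2. Check that the eligibility checklist carries the same interval.
3. Change the lung disease row of Table 4.1.3.2:1 to any grade, with permanent discontinuation, so that the rule for unlisted grade 2 events cannot apply.
4. Leave diarrhea alone, or state once whether the footnote 2 exception applies to both diarrhea (4.2.3.1) and grade 3 rash (4.2.3.3). Do not simply delete the footnote from the diarrhea row: its action text appears to be shared with the nausea/vomiting and renal rows.

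**Cost.** Wording in one amendment and a check of the checklist, with no added patients or visits. Choosing 4 weeks delays some recently irradiated candidates by up to 14 days. Stating the interval in the exclusion list lets sites time screening so that tests do not expire.

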3.3.3.7 Pre-existing interstitial lung disease

3.3.3.8 Inability to take oral medications

3.3.3.9 Prior therapy with afatinib

### **3.3.4 Removal of patients from therapy or assessments**

In the absence of treatment delays due to adverse event(s), treatment may continue until

one of the following criteria applies:

- Disease progression,
- Intercurrent illness that prevents further administration of treatment,
- Pregnancy,
- Unacceptable adverse event(s),
- Patient decides to withdraw from the study,
- General or specific changes in the patient's condition render the patient unacceptable for further treatment in the judgment of the investigator.

### **3.3.5 Specifics regarding tumor testing for study enrollment**

Analysis of results of tumor somatic testing from a CLIA-certified laboratory is required for study eligibility determination. Such testing may have been performed historically (previously), or testing may be conducted specifically for the purposes of study eligibility screening. If the latter, it is encouraged that patients consider signing the consent in advance of desired study entry so as to allow time for tumor results to become available (tissue pre-screening). It is permissible to consent patients even while they are receiving other anti-cancer therapy as long as such patients have unresectable metastatic urothelial carcinoma. Patients without measurable metastatic disease are not eligible for genomic pre-screening under the auspices of this study. A central (sponsor-provided) CLIA-certified laboratory is available to conduct tumor sample pre-screening for this study. If testing is sought through this dedicated (sponsor-provided) central laboratory, a turn-around time of at least 14 days from the time of receipt of the sample should be expected. If a result from a local CLIA-certified laboratory is proposed for eligibility screening, the local laboratory must be first approved by the central study PI. No new (fresh) tumor biopsies should be sought under the auspices of this study, however such biopsies may of course be performed for standard of care reasons or if felt to be clinically appropriate as part of routine care in the view of the treating physician.

## **4. TREATMENTS**

### **4.1 TREATMENTS TO BE ADMINISTERED**

Patients will receive afatinib.

#### **4.1.1 Identity of investigational product**

**Substance (INN): afatinib**

#### **4.1.2 Selection of doses in the study**

All patients will receive afatinib at a starting dose of 40 mg/day given continuously.

#### **4.1.3 Drug assignment and administration of doses for each patient**

##### **4.1.3.1 Afatinib**

For administrative purposes treatment will be divided into treatment courses, which are each 8 weeks (56 days) in duration. Patients will take a single oral dose of 40 mg afatinib each day (56 days/cycle). All patients will start with 40 mg tablets and in the event that dose reduction is necessary, the patient will return to the clinic and new medication will be dispensed.

Dose reductions should be performed according to Table 4.1.3.2:1.

The medication should be taken at approximately the same time each day ( $\pm$  2 hours) and should be taken without food (i.e. afatinib should be taken at least 1 hour before or at least 2 hours after a meal).

Missed doses of afatinib can be made up if taken within 6 hours of the regularly scheduled time. Otherwise, the dose should be skipped and patients should take the next scheduled dose at the usual time. Patients with emesis should not take a replacement dose.

